5.5.1.1.11. HBV Flares

The criteria based on blood markers/lab tests for each of the flare types are defined as below.

a) HBV Virologic flare is defined as follows:

Derivation 1. This derivation of virologic flare will be assessed only for those participants who are off-treatment and had HBV DNA <LLOQ at the last observed point on-treatment.

The start date of a confirmed virologic flare is defined as the first date of two consecutive visits with HBV DNA > 200 IU/mL. The end date of the same confirmed virologic flare is defined as the first date when HBV DNA value returns to ≤ 200 IU/mL or the date of treatment restart (ie JNJ-3989 and/or NA), whichever comes first. Each virologic flare will be categorized based on the confirmed (ie two consecutive values) peak HBV DNA above any of the three thresholds within the start and end date of that flare as follows: 20,000 IU/mL 2,000 IU/mL and 200 IU/mL.

- 1 (Yes) = confirmed HBV DNA > peak threshold
- 0 (No) = at least one off-treatment HBV DNA measurement available and not meeting the criteria of confirmed HBV DNA > peak threshold.
- 2 (Not applicable) = no off-treatment HBV DNA quantitative measurements available.

Derivation 2. This derivation of virologic flare will be assessed only for those participants who are off-treatment and had HBV DNA \geq LLOQ at the last observed point on-treatment.

The start date of a confirmed virologic flare is defined as the first date of two consecutive visits with HBV DNA log₁₀ increase > 1 log₁₀ from EOT. The end date of the same confirmed virologic flare is defined as the first date when HBV DNA log₁₀ increase from EOT returns to \leq 1 log₁₀ or the date of treatment restart (ie JNJ-3989 and/or NA), whichever comes first. Each virologic flare will be categorized based on the confirmed (ie, two consecutive values) peak HBV DNA increase above any of the three thresholds within the start and end date of that flare as follows: 1 log₁₀, 2log₁₀, 3 log₁₀.

- (Yes) = confirmed HBV DNA increase from EOT > peak threshold
- 0 (No) = at least one off-treatment HBV DNA measurement available and not meeting the criteria of confirmed HBV DNA increase from EOT > peak threshold.
- 2 (Not applicable) = no off-treatment HBV DNA quantitative measurements available.

b) Off-treatment HBV biochemical flare is defined as follows:

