The start date of a confirmed off-treatment biochemical flare is defined as the first date of two consecutive visits with ALT and/or AST \geq 3x ULN and \geq 3x nadir (ie, lowest value observed up to the start of the flare). The end date of the same off-treatment biochemical flare is defined as the first date when there is a 50% reduction from the peak ALT and/or AST level or the date of treatment restart (ie JNJ-3989 and/or NA), whichever comes first.

- 1 (Yes) = confirmed ALT and/or AST \geq 3x ULN and \geq 3x nadir (ie, lowest value observed up to the start of the flare)
- 0 (No) = otherwise

c) On-treatment HBV biochemical flare is defined as follows:

The start date of a confirmed on-treatment biochemical flare is defined as the first date of two consecutive visits with ALT and/or AST \geq 3x ULN and \geq 3x nadir (ie, lowest value observed up to the start of the flare). The end date of the same on-treatment biochemical flare is defined as the first date when there is a 50% reduction from the peak ALT and/or AST level, regardless of stopping JNJ-3989 and/or NA.

- 1 (Yes) = confirmed ALT and/or AST \geq 3x ULN and \geq 3x nadir (ie, lowest value observed up to the start of the flare)
- 0 (No) = otherwise

d) HBV Clinical flare is defined as follows:

A HBV clinical flare occurs either when a HBV virologic flare and off-treatment HBV biochemical flare overlap in time or when a HBV biochemical flare starts within 4 weeks following the end of a HBV virologic flare.

The start date of a HBV clinical flare is defined as the minimum start date of the HBV virologic flare and HBV biochemical flare. The end date of a HBV clinical flare is defined as the maximum end date of the HBV virologic flare and HBV biochemical flare, ie, the later date between HBV DNA returns to ≤ 200 IU/mL (or $\leq 1 \log_{10}$) and 50% reduction from the peak ALT and/or AST level reached during the HBV biochemical flare.

- 1 (Yes) = confirmed HBV DNA $>$ peak threshold (for derivation 1 of virologic flare) or HBV DNA increase from end of treatment $>$ peak threshold (for derivation 2 of virologic flare) and confirmed ALT and/or AST $\geq 3x$ ULN and $\geq 3x$ nadir (ie, lowest value observed up to the start of the flare)
- 0 (No) = otherwise

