5.5.2.1.4. HBV Flares

The incidence rate will be calculated and summarized for each type of on-treatment or off-treatment flares (virologic, biochemical and clinical) separately, as well as the overall incidence of participants experiencing at least one flare, regardless of type. Additionally, for each participant the total number of flares the participant experienced will be counted by type. Such counts will be used to summarize the distribution of the total number of flares by type and by intervention arm.

For on-treatment biochemical flares, the incidence of flares causing treatment discontinuation will be summarized. Further, for off-treatment flares, the count and percentage of participants who experienced a flare followed by NA re-treatment will be summarized by flare type. Similarly, the incidence of flares followed by the achievement of HBsAg seroclearance (at any time) will be summarized by flare type. Flares that are associated with signs of liver decompensation will be provided in a listing.

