2. Confirmed ≥ 2 grade level increase from baseline in graded proteinuria
3. Confirmed ≥ 1 grade level increase from baseline in graded hypophosphatemia
4. Confirmed ≥ 1 grade level increase from baseline in graded glycosuria concurrent with serum glucose ≤ 100 mg/dL (normoglycemic glycosuria)

A confirmed laboratory abnormality is defined as an abnormality observed at 2 consecutive post-baseline measurements or an abnormality observed at 1 measurement followed by study drug discontinuation

A subclinical renal proximal tubulopathy will be defined as confirmed abnormalities in any 2 out of the 4 renal parameters (serum creatinine and one or more of the 3 other markers of tubular dysfunction).

Baseline Subclinical renal proximal tubulopathy

Potential Markers of Renal Proximal Tubulopathy at Baseline

1. Grade ≥ 1 serum creatinine
2. Grade ≥ 2 proteinuria
3. Grade ≥ 1 hypophosphatemia
4. Grade ≥ 1 glycosuria concurrent with serum glucose ≤ 100 mg/dL (normoglycemic glycosuria)

A baseline subclinical renal proximal tubulopathy will be defined as abnormalities in any 2 out of the 4 renal parameters (serum creatinine + 1 or more of the 3 other markers of tubular dysfunction).

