10	Received wrong treatment of study drug JNJ-3989: incorrect dose or placebo when randomized to active (and vice versa)	Received wrong treatment or incorrect dose	Yes
11	Subject did not receive dose of study drug JNJ-3989/placebo within window: Subject missed two consecutive injections or missed more than 2 injections.	Received wrong treatment or incorrect dose	Yes
12	Subject missed NA treatment for more than 5 doses within a four week period.	Received wrong treatment or incorrect dose	Yes
13	Subject received expired study medication <JNJ-3989, NA or placebo>.	Received wrong treatment or incorrect dose	Yes
14	Subject has event of signs of decreasing liver function based on laboratory or	Received wrong treatment or incorrect	Yes

Sequence No.	Protocol Deviation Description (DVTERM)	Protocol Deviation Coded Term (DVDECOD)	Intercurrent Event
	clinical findings, but did not start NA treatment.	dose	
15	Subject has confirmed signs of hepatic decompensation <specify> but subject continued study treatment.	Developed withdrawal criteria but not withdrawn	Yes
16	The subject has confirmed HBV virological breakthrough but continued study treatment.	Developed withdrawal criteria but not withdrawn	Yes
17	Accidental unblinding of treatment group of a subject or a blinded staff member prior to planned unblinding at <specify visit>.	Other	No
18	Study < specify the visit which >procedure not done at scheduled Visits.	Other	No
19	Efficacy evaluation of HDV RNA not done at Week 48 Visit	Other	No
20	Efficacy evaluation of ALT not done at Week 48 Visit	Other	No
21	Efficacy evaluation of LSM not done at Week 48 Visit	Other	No
22	Efficacy evaluation of HBsAg not done at Week 48 Visit	Other	No
23	Study Visits not performed per protocol.	Other	No

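### SAP 5.5.1.1.11: a virologic flare seen at only one visit before treatment restart is coded No, and the confirmation of biochemical flares across a restart is undefined

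*SAP*

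**What the plan says.** **Virologic flare (SAP 5.5.1.1.11 a).** Derivation 1 reads: "The start date of a confirmed virologic flare is defined as the first date of two consecutive visits with HBV DNA > 200 IU/mL". Derivation 2 has the same structure, using a rise of more than 1 log10 from EOT. In both, the flare ends when the value falls back or at "the date of treatment restart (ie JNJ-3989 and/or NA), whichever comes first". Each flare is then categorised by a peak that must be confirmed, glossed as two consecutive values, between the flare's start and end dates. Code 0 (No) applies to anyone who has at least one off-treatment HBV DNA value but no such confirmation.

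**Off-treatment biochemical flare (b).** "The start date of a confirmed off-treatment biochemical flare is defined as the first date of two consecutive visits with ALT and/or AST" at least 3x ULN and at least 3x nadir. It ends at a 50% fall from peak "or the date of treatment restart (ie JNJ-3989 and/or NA), whichever comes first".

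**Clinical flare (d).** Either a virologic and an off-treatment biochemical flare overlap, or a biochemical flare starts within 4 weeks after a virologic flare ends. Section 5.5.1.1.11 closes by limiting virologic and clinical flares to the off-treatment period.

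**General rules (5.5).** For HBV endpoints, off-treatment means receiving neither JNJ-3989/placebo nor NA. A criterion is confirmed at two or more consecutive time points, or at the last observed one.

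**Reporting (5.5.2.1.4).** For off-treatment flares, "the count and percentage of participants who experienced a flare followed by NA re-treatment will be summarized by flare type".

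**The concern.** Restarting treatment is a natural response to a flare, and here it also closes the window in which the flare must be confirmed. If restart falls between the first and second qualifying visits, the event that may have prompted it can go unrecorded.

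The SAP allows for restarts. Section 4.1 lists NA re-treatment, 4.6 separates out participants who never restarted NA, and 5.5.2.1.4 tabulates flares followed by re-treatment. Attachment 1, item 14 ("Subject has event of signs of decreasing liver function based on laboratory or" clinical findings, with NA not started) treats a failure to start NA in that situation as a major deviation.

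The post-treatment HBV flare proportion is a listed secondary endpoint (1.1). The re-treatment summary is the output most exposed, because only participants who restarted can enter it.

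**Working it through.** The SAP gives no figure to reproduce; this is a check of how the definitions behave.

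**1. Room for a restart between visits.** The Table 2 follow-up target days are 15, 29, 43, 57, 85, 113, 141, 169, 211, 253, 295 and 337. The differences are 14 days up to FU Week 8, 28 days up to FU Week 24 and 42 days up to FU Week 48. Scheduled visits are thus 2, 4 and then 6 weeks apart.

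**2. Virologic flare, invented profile.** HBV DNA is 5 IU/mL at FU Week 20, 50,000 at Week 24, 1,500 at Week 30 and 50 at Week 36. NA is restarted shortly after Week 24.
- Weeks 24 and 30 both exceed 200 IU/mL, so on a lenient reading a start date exists at Week 24.
- The end date is the restart, so the window holds only the Week 24 value.
- The peak needs two values inside the window, and there is one. The participant has an off-treatment measurement, so the code is 0 (No), not 2 (Not applicable).
- Both routes to a clinical flare need a virologic flare, so neither is available.

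**3. Biochemical flare, invented profiles.** ALT is 0.8x ULN (nadir) at FU Week 20 and 12x ULN at Week 24, with NA restarted shortly after Week 24. The 3x nadir limit is 3 x 0.8 = 2.4x ULN, so 3x ULN is the binding criterion. Three readings are possible:
- A: both visits must precede restart.
- B: only the first visit must precede restart.
- C: the last off-treatment value counts as the last observed time point of Section 5.5.

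| ALT after Week 24 (x ULN) | A | B | C | On-treatment flare | ALT/AST elevation (5.5.1.1.12) |
|---|---|---|---|---|---|
| Week 30: 2; Week 36: 1 | No | No | Yes | No | No |
| Week 30: 5; Week 36: 1 | No | Yes | Yes | No | Yes |
| Week 30: 8; Week 36: 4; Week 42: 1 | No | Yes | Yes | Yes | Yes |
| Second row's values, no restart | Yes | Yes | Yes | No | Yes |

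Without restart the readings agree; with restart they do not. In the third row, reading A yields only an on-treatment flare, while B and C let one episode count as both off-treatment and on-treatment.

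**4. Does Section 5.5 settle it?** Not clearly. The flare section defines confirmation itself, as two consecutive values. Restarted participants also remain under observation, so their pre-restart value is not literally the last observed one. Reading C works only if last observed is taken to mean last off-treatment, which the SAP does not say.

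**5. Size.** The number stopping NA, and the number restarting between two visits, are not given. What follows from the SAP is a minimum shift per missed participant. With at most 52 participants in the study and 30 in Part 2 (1.2), each one lowers the proportion by at least 1/52 = 1.9 percentage points overall, or 1/30 = 3.3 points in Part 2. The shift is larger if the denominator is restricted to one arm or to participants off NA.

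**The case against.** A reader might infer that every flare treated after one abnormal visit goes uncounted. The SAP does not support that. For biochemical flares, restart only sets the end date; nothing requires the second visit to precede it, and ALT may still qualify at that visit. The last-observed clause could also be read as confirming the event.

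A reader might also infer that the lost flares are the most serious, that losses are certain, or that the arm restarting sooner will look better. The SAP has no data linking speed of restart to severity. The 5.5.2.1.4 summary is compatible with restart after confirmation, and item 14 does not mention a restart after a single flare visit. A retest rule in the protocol, which was not available for this review, could make the situation rare. The flare section says visits, not scheduled visits, so an early unscheduled repeat could confirm a flare before restart.

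Follow-up efficacy is descriptive (section 5). ALT signals also appear in worst-grade tables that use single and unscheduled values (6.2), in adverse events of special interest (6.1.3) and in the DRC's monitoring (3.1.1). Two-visit confirmation is a reasonable filter for isolated values. The renal rule in 6.3.2, which accepts "an abnormality observed at 1 measurement followed by study drug discontinuation", concerns another endpoint and discontinuation rather than restart; it is a precedent, not an inconsistency.

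All of this limits the point without removing it. The virologic window still excludes the one-visit case. The ALT/AST elevation endpoint also needs two visits and misses the fast-falling profile. None of the other outputs feeds the flare-followed-by-re-treatment summary.

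**Conclusion.** The point holds in a limited form. For virologic flares, and clinical flares that depend on them, the flare section's wording codes one qualifying value followed by restart as No. For off-treatment biochemical flares the outcome is undefined: counted, missed or classed as on-treatment, depending on the reading. Sections 5.5 and 5.5.1.1.11 give conflicting meanings of confirmed and need to be reconciled.

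The off-treatment flare proportions and the re-treatment summary may therefore be biased downward, by an amount that cannot be computed from the SAP. The conclusion assumes that at least some restarts fall between a first qualifying visit and the next, and, for virologic flares, that the flare section's two-value rule takes precedence over the general clause. No hypothesis test is affected, but a listed secondary endpoint is, and in a study of this size a single participant moves it visibly.

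**What to change.** Change the analysis derivation in 5.5.1.1.11 a), b) and d), and reconcile it with Section 5.5:

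- Keep the two-visit flare as it is.
- Also derive a restart-confirmed flare: the criterion is met at the last off-treatment visit before restart of JNJ-3989 and/or NA. The start date is that visit and the end date is the restart. Carry the label through to clinical flares.
- State whether an ALT/AST value taken after restart can confirm an off-treatment biochemical flare.
- State whether the last-observed alternative in Section 5.5 applies to flares.
- In 5.5.2.1.4, report two-visit and restart-confirmed flares on separate lines, including in the re-treatment summary.

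The cost is a few sentences of SAP text and a small programming change. The downside is that some isolated abnormal values followed by restart will be counted; the separate line keeps them visible. Nothing about when treatment is stopped or restarted changes.

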5.5. Other Secondary Endpoints

Other secondary endpoints will be summarized descriptively by intervention arm, by study phase (unless specified otherwise), timepoint and study part. No imputation rule will be used in case of missing data and the analysis will be based on observed cases. Statistical analyses of selected other secondary endpoints will be done with no adjustment for multiplicity.

The following on and off-treatment periods will be used for all secondary efficacy endpoints:

- For all HBV endpoints:
 - **On-treatment** will be defined as the time periods in which the participant receives any of the study interventions (JNJ-3989/placebo and/or NA).
 - **Off-treatment** will be defined as the periods when the participants do not receive any of the study interventions (JNJ-3989/placebo and NA).
- For all HDV endpoints:
 - **JNJ-3989 on-treatment** will be defined as the time period in which the participant receives JNJ-3989/placebo (regardless of continuing NA treatment).
 - **JNJ-3989 off-treatment** will be defined as the time period in which the participant is not receiving JNJ-3989 (regardless of continuing NA treatment).

The following on and off-treatment nadirs will be used for all secondary efficacy endpoints:

- **On-treatment nadir** will be defined as the lowest value during the on-treatment period up to the time of assessment.
- **JNJ-3989 on-treatment nadir** will be defined as the lowest value during the JNJ-3989 on-treatment period up to the time of assessment.
- **Off-treatment nadir** will be defined as the lowest value during the off-treatment period up to the time of assessment.
- **JNJ-3989 off-treatment nadir** will be defined as the lowest value during the JNJ-3989 off-treatment period up to the time of assessment.
- **Overall nadir** will be defined as the lowest value collected during the study up to the time of assessment.

A confirmed criteria means that the criteria should be fulfilled at 2 or more consecutive time points or at the last observed time point.

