5.5.1.1.5. JNJ-3989 Off-treatment HDV Clinical Flares

An JNJ-3989 off-treatment HDV clinical flare is defined as a confirmed increase in HDV RNA of $> 1 \log_{10}$ IU/mL above the LLOQ JNJ-3989 off-treatment and confirmed ALT and/or AST $\geq 3x$ ULN and $\geq 3x$ JNJ-3989 off-treatment nadir during the follow-up phase.

The start date of an JNJ-3989 off-treatment HDV clinical flare is defined as the minimum date between the date when the confirmed HDV RNA criterion is met and start date of the JNJ-3989 off-treatment biochemical flare.

The end date of a JNJ-3989 off-treatment HDV clinical flare is defined as either:

- The maximum date between HDV RNA increase returns to $\leq 1 \log_{10}$ IU/mL and the date when a 50% reduction from the peak ALT and/or AST level is reached.
- Or the date of JNJ-3989 treatment restart, whichever comes first.
 - 1 (Yes)= confirmed HDV RNA of $> 1 \log_{10}$ IU/mL above the LLOQ JNJ-3989 off-treatment and confirmed ALT and/or AST $\geq 3x$ ULN and $\geq 3x$ JNJ-3989 off-treatment nadir

- 0 (No) = otherwise
- 2 (Not applicable) = no JNJ-3989 off-treatment HDV RNA and/or ALT/AST quantitative measurements available.

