The HBV virologic and clinical flares will be assessed only off-treatment, while biochemical flares will be identified on-treatment and off-treatment, respectively. On-treatment virologic flares are described as virologic HBV breakthrough in Section [5.5.1.1.9](#).

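### Off-treatment HBV biochemical flares (and, less clearly, clinical flares) have no Not applicable code, so as written participants who are never off treatment count as flare-free

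*SAP*

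**What the plan says.** SAP 5.5 defines off-treatment for HBV endpoints: it "will be defined as the periods when the participants do not receive any of the study interventions", meaning both JNJ-3989/placebo and NA. Anyone who stays on NA through follow-up therefore never has an off-treatment period for these endpoints.

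Section 5.5.1.1.11 then codes each flare type:

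- Virologic flare (a): No requires at least one off-treatment HBV DNA measurement, and there is a third level, "2 (Not applicable) = no off-treatment HBV DNA quantitative measurements available".
- Off-treatment biochemical flare (b): Yes, or "0 (No) = otherwise". There is no third level.
- Clinical flare (d): the same two levels as (b).

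The HDV clinical flare in 5.5.1.1.5 also uses a catch-all No, but adds "2 (Not applicable) = no JNJ-3989 off-treatment HDV RNA and/or ALT/AST quantitative measurements available".

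After the definitions, 5.5.1.1.11 adds: "The HBV virologic and clinical flares will be assessed only off-treatment, while biochemical flares will be identified on-treatment and off-treatment, respectively". For the summary, 5.5.2.1.4 says: "The incidence rate will be calculated and summarized for each type of on-treatment or off-treatment flares (virologic, biochemical and clinical) separately". It names no denominator.

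**The concern.** The catch-all No in (b) and (d) takes in two kinds of participant who could not have had the event: those with no off-treatment period, and those with no ALT/AST taken during one. If they enter the denominator, the off-treatment flare proportion no longer describes people who stopped all treatment. It becomes a mixture that depends on how many stayed on NA.

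The flare types also stop being comparable. A clinical flare requires a virologic flare, yet the virologic proportion would leave out participants without off-treatment data while the biochemical proportion, and possibly the clinical one, would include them as No. Off-treatment HBV flare of all three types is a listed secondary endpoint (SAP 1.1). With 52 participants in total, a few people reclassified would move the percentage visibly.

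**Working it through.** The SAP gives no flare rate, so there is no figure to reproduce. The check sets the rules side by side and then works out the effect algebraically.

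**Step 1. Is the missing level specific to (b) and (d)?**

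| Endpoint | Yes | No | Not applicable |
|---|---|---|---|
| HBV virologic flare (a) | 1 (number not printed in Derivation 2) | needs an off-treatment measurement | 2 |
| Off-treatment HBV biochemical flare (b) | 1 | otherwise | none |
| HBV clinical flare (d) | 1 | otherwise | none |
| HDV clinical flare (5.5.1.1.5) | 1 | otherwise | 2 |

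It is, among the off-treatment flare definitions. The on-treatment biochemical flare (c) also lacks the level, but every ITT participant has received study intervention and so has an on-treatment period.

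**Step 2. Can participants be without an off-treatment period?** Yes. Section 4.6 assigns zero follow-up NA exposure only to those who stopped NA at Week 144/148 and never restarted, and provides a formula for NA exposure in follow-up for the others. Sections 5.5.1.1.6 and 5.6.1.1.2 likewise allow for NA continuing after JNJ-3989 stops.

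**Step 3. Does another rule remove them?**

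- The default efficacy set is ITT (Section 5), and 5.5.2.1 asks for the number and proportion of participants. Neither restricts to those off treatment.
- The observed-case rule (5.5, 5.5.2) drops missing values. A catch-all No supplies a value of 0, so nothing is missing.
- Where the SAP wants a restricted off-treatment denominator it writes one (5.6.2.1.1 and 5.6.2.1.2). Section 5.5.2.1.4 has none.

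**Step 4. Size of the effect under the literal reading.** Let N be all participants, k those ever off treatment with assessments, and e the flares among them.

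- As coded: e / N
- Among those assessable: e / k
- Ratio: (e / N) / (e / k) = k / N, the share ever off treatment

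Input from the SAP: N = 52 (Section 1.2). Assumptions, because the SAP gives neither: k, shown over a range, and a flare proportion of about 30% among those off treatment.

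| k | e | e / k | e / 52 | k / 52 |
|---|---|---|---|---|
| 13 | 4 | 30.8% | 7.7% | 0.25 |
| 26 | 8 | 30.8% | 15.4% | 0.50 |
| 39 | 12 | 30.8% | 23.1% | 0.75 |
| 52 | any | e / 52 | e / 52 | 1.00 |

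The assumed 30% does not affect the ratio, which depends only on k / N. The same ratio applies within an arm or part, using that group's own k and N.

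**The case against.** The strongest reply is that the codes are shorthand and their context limits them. Item (b) is headed as an off-treatment flare. Its Yes code does not repeat that restriction either, yet nobody would count an ALT rise during NA as an off-treatment flare, so the heading could limit the No code in the same way. For (d), the sentence after the definitions confines assessment to the off-treatment period, and (d) depends on a virologic flare that is itself assessed only in participants off treatment. Section 5.5.2.1.4 states no denominator, so the use of all participants is an inference.

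Part of this stands. For (d), a programmer could reasonably exclude participants who were never off treatment, and the point is correspondingly weaker. For (b), the heading says which ALT/AST values count, and the later sentence says only that biochemical flares are identified in both periods. Neither says what to do with a participant who has no such values, and the written code gives that participant a 0.

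Three stronger readings are tempting and are not supported:

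- A reader might infer that the SAP sets the flare denominator to all participants. It sets none; dilution follows from the literal coding combined with the ITT default.
- A reader might infer that the trial's main safety evidence on stopping NA is compromised. The SAP lists these flares under anti-HBV efficacy in follow-up. Adverse events, laboratory tests and adverse events of special interest, including ALT/AST elevations, are analysed separately in Section 6. The number of flares, those followed by NA re-treatment, and the listing of flares with signs of decompensation do not depend on the missing code.
- A reader might infer from the Yes code in (d) that HBV DNA and ALT rises far apart in time would count together. The definition just above that code already requires overlap, or onset of the biochemical flare within 4 weeks after the virologic flare ends.

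**Conclusion.** The coding is inconsistent and should be corrected. For the off-treatment biochemical flare no other text repairs it; for the clinical flare the text limits the problem without resolving it. Under the literal coding and the ITT default, the off-treatment flare proportion is multiplied by the share of participants ever off treatment, and it rests on a different population from the virologic flare proportion.

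The size is unknown because the SAP does not say how many participants stop NA. There is no effect if all of them do, or if no flares occur. The tabulated percentages are illustrations, not predictions, and no direction of bias between arms can be derived from the SAP. The consequence is confined to descriptive secondary endpoints.

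**What to change.** 1. In 5.5.1.1.11 (b), add a code 2, Not applicable, for participants with no off-treatment ALT/AST measurement.
2. In 5.5.1.1.11 (d), add a code 2 for participants with no off-treatment HBV DNA and/or ALT/AST measurement, matching the HDV clinical flare.
3. In 5.5.2.1.4, state that off-treatment flare incidence is calculated over participants coded 0 or 1, and show that number beside each percentage. The on-treatment flare (c) needs no change.
4. Optionally, and only for clarity, repeat the overlap or within-4-weeks condition in the Yes code of (d).

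The cost is SAP wording and one denominator flag in programming; no new data are needed. Denominators become smaller if some participants are never off treatment or lack the measurements. Where flares have also occurred, the reported percentages will be higher and their confidence intervals will rest on fewer people.
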